5.2.2 Clinical Chemistry

Clinical chemistry results will be summarised in the same way as the hematology data. The box and whisker plot will present the results for the following parameters: triglycerides, total cholesterol, total bilirubin, cystatin C and creatinine.

The separate summaries described for presentation of platelets will be presented in relation to triglycerides. However, these summaries will be adjusted to relate to increase in triglycerides. Therefore, time to nadir will be replaced with time to first maximum value post-baseline, and references in the definitions to 'minimum', 'decrease' or 'below lower limit of normal' should be replaced with 'maximum', 'increase' and 'above the upper limit of normal' respectively. The summary of platelet data described for subjects in the safety analysis set who reduced dose due to platelet count decrease will instead be a summary for subjects in the safety analysis set who reduced dose due to triglyceride increase.

A plot of the mean triglyceride count at each visit will be produced by treatment group.

All clinical chemistry values will be listed, flagging all abnormal findings.

Data for the following liver function parameters will also be listed separately: Aspartate aminotransferase (AST), Alanine aminotransferase (ALT), Gamma-glutamyl transpeptidase (GGT).

5.2.3 Urinalysis

All urinalysis values will be listed, flagging all abnormal findings where reference ranges are available.

5.2.4 Coagulation

Summary statistics of observed coagulation results and change from baseline will be presented in the same way as the hematology data. A shift table of coagulation results will also be presented as described for the hematology data.

All coagulation values will be listed, flagging all abnormal findings.

5.2.5 Serology

All serology data will be listed in full.

5.3 Vital Signs

Summary statistics of vital sign observed values and change from baseline by parameter and visit will be presented by treatment group for all subjects in the safety analysis set.

All vital sign data will be listed in full.

5.4 Physical Exams

Details regarding whether or not a physical examination occurred, as well as the date of assessment, will be listed.

5.5 Electrocardiography

Clinical interpretations of standard 12-lead ECG assessments will be summarised as follows. Shift in ECG interpretation from baseline to each visit for normal, abnormal NCS, abnormal CS, missing and total results will be summarised by treatment group for all subjects in the safety analysis set using the “worst case” scenario for each set of triplicate readings as required. Subjects will only be included in the missing category if they attended the visit but have no data available for the ECG interpretation. Withdrawn subjects will not be included in the missing category. This shift summary will be repeated for the ECG interpretation as recorded on the CRF by the investigator and the interpretation recorded by the laboratory.

Summary statistics of observed values and change from baseline will be presented by visit and treatment group for all subjects in the safety analysis set for the following parameters:

- RR interval (msec)
- PR interval (msec)
- QRS duration (msec)
- QT interval (msec)
- QTcF interval (msec) [Fridericia's formula for QTcF (Fridericia, 1920)]
- QTcB interval (msec) [Bazett's formula for QTcB (Bazett, 1920)]
- ECG mean ventricular rate (beats/min)

Where triplicate ECG assessments have been performed, the mean of the non-missing values will be used in the analyses.

The mean QTcF values will be plotted over time for each treatment group.

The incidence of outliers in QTcF intervals (>450, >480, and >500 msec), and the change from baseline in QTcF intervals (>30 and >60 msec) will be summarized by visit and overall for each treatment group as defined in ICH E14 guideline (ICH_E14, 2005). As above, where triplicate ECG assessments have been performed, the mean of the non-missing values will be used to determine outliers. A subject will be counted once for each outlier in the overall summary if they experienced at least one occurrence of that outlier.

All ECG interpretations will be listed. Any comments collected with the ECG data will not be presented in the listing but will be retained in the data for reference.

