10. Have platelets count, White Blood Cell and Hemoglobin at screening  $<$  Lower Limit of Normal (LLN) (for abnormal screening laboratory test results ( $<$ LLN), the platelets count, White Blood Cell and Hemoglobin will be repeated once; if the repeat test result is still  $<$ LLN, then exclusionary);
11. Have symptomatic cardiomyopathy or heart failure (New York Heart Association Class III or IV) or left ventricular ejection fraction  $< 50\%$  at screening;
12. Have a current or history of liver disease or impairment, including but not limited to an elevated total bilirubin (i.e.  $> 1.5 \times$  ULN), unless secondary to Gilbert disease or pattern consistent with Gilbert's;
13. Have inadequate renal function, as defined by serum Cystatin C  $> 2 \times$  the upper limit of normal (ULN). If the value is  $> 2 \times$  ULN, the serum Cystatin C will be repeated once; if the repeated test result is still  $> 2 \times$  ULN, the subject should be excluded);
14. Have Triglycerides  $> 300$  mg/dL (3.42 mmol/L) in fasting condition at screening visit;
15. Have a positive test for hepatitis B surface antigen, hepatitis C antibody, or human immunodeficiency virus at screening;
16. Have a baseline corrected QT interval, Fridericia's correction (QTcF)  $> 450$  msec, (as the mean of 3 consecutive readings 5 minutes apart) or history of additional risk factors for torsades de pointes (e.g., heart failure, hypokalemia, or family history of long QT syndrome);
17. Have a psychiatric illness/social situations rendering the potential subject unable to understand and comply with the muscle function tests and/or with the study protocol procedures;
18. Have any hypersensitivity to the components of study medication;
19. Have a sorbitol intolerance or sorbitol malabsorption, or have the hereditary form of fructose intolerance;
20. Have contraindications to MRI or MRS (e.g., claustrophobia, metal implants, or seizure disorder).

At the discretion of the Investigator, subjects not meeting inclusion/exclusion criteria may be re-screened twice with an interval of at least 3 months between assessments.

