6. 12-lead ECG has to be done in triplicate at the screening visit and during the other visits if an ECG demonstrates a prolonged QTcF interval  $>$  450 msec, obtain 2 more ECGs over a brief period, and then use the averaged QTcF values of the 3 ECGs to determine whether the subjects should be discontinued from the study (see Section 7.3.1). 12-lead ECG should be performed at 2,5 hours (i.e 150 minutes)  $\pm$ 30 minutes after drug intake.
7. Pulmonary function tests FEV1, FVC, FEV1/FVC and PEF. In case the test does not achieve ATS criteria and the evaluator does not feel a valid attempt has been made, the subject should repeat the test at randomization if the test is failed at screening visit. If the test is failed at 12 months and/or at 18 months the subject has to be asked to come back to perform the test.
8. Serology: immunoassay methodology for CMV IgM; in-house methodology of chemiluminescence for HBsAg/HCV/HIV; and ECLIA for EBV IgG.
9. Hematology test: CBC:RBC, WBC (including differential count), hemoglobin, MCH, MCHC, MCV, hematocrit, and platelets. Test will be done according to the schedule (i.e., weekly for the first month of treatment, every 2 weeks for the second month of treatment) and are to be performed more frequently if clinically indicated. Note: Repeat visits for the platelets count will be assumed at the request of the Investigator. If the dose is reduced due to platelet count  $\leq$ 150 x 10^9/L, and/or white blood cell  $<$ 3.0 x 10^9/L and/or hemoglobin  $<$ 10.0 mg/dL, a complete blood count (i.e.CBC) test must be performed weekly for 8 consecutive weeks.
10. The following blood tests will be assessed: total bilirubin, direct bilirubin, alkaline phosphatase, amylase, ALT, AST, LDH, cystatin C, CRP, GGT, creatine kinase, total protein, albumin, uric acid, triglycerides, phosphorus, total cholesterol, LDL, HDL, sodium, potassium, chloride, calcium, glucose, creatinine, BUN, TSH, fT3, fT4, bicarbonate). Note that TSH, fT3, and fT4 will be taken at Visits 7, 9, 10, 11, 12, 13, 14, 15 and 16.
11. Urinalysis: appearance, pH, specific gravity, protein, glucose, ketone bodies, blood and WBCs, and urobilinogen.

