### 9.1.1 Visit 1 and Visit 2 - Screening (*Week -4 ± 2 weeks*)

The Screening visits (Visit 1 and Visit 2) will occur within 4 weeks ( $\pm 2$  weeks) prior to the Randomisation Visit. The following assessments will be performed at Visit 1 unless noted otherwise:

- Obtain written Informed Consent from the subject's parent/legal guardian and assent or consent from the subject, if applicable;
- Eligibility criteria: review inclusion and exclusion criteria;
- Genetic test (*only if it is not already available*);
- Collect medical history and demographic data;
- Collect and record prior medications (taken in the past 6 months);
- Perform a physical examination (at Visit 1 assessment for ankle ROM should be done);
- Measure vital signs (blood pressure, pulse rate, and body temperature);
- Measure weight;
- Measure height;
- Perform a 12-lead ECG (in triplicate);
- Perform an ECHO;
- Perform pulmonary function tests: FEV1, FVC, FEV1/FVC, and PEF;
- Collect blood samples for:
  - serology tests;

- hematology;
- blood chemistry;
- coagulation tests (prothrombin time [PT] and activated partial thromboplastin time [aPTT]);
- Obtain a urine sample for urine analysis;
- Perform Quality of Life tests (using Paediatric Outcomes Data Collection Instrument [PODCI] scores);
- Perform time to 4SC (the test should be performed at Visit 1 and at Visit 2; the 4SC at Visit 2 can be performed one day after V1 up to a maximum of 2 weeks +3 days);
- Perform NSAA and 6MWT;
- Perform muscle strength test (both by HHM and MMT);
- Perform cognitive function evaluation: Raven coloured progressive matrices (at Visit 1 or at Visit 2. Test should be performed at the beginning and at the end of the study at the same time of the day);
- Assess AEs;
- If all inclusion and exclusion criteria have been met and the subject is eligible, the following assessments must be performed at Visit 2 to conclude the screening period before the randomisation:
  - MRI/MRS

At Visit 1, functional tests will be video recorded.

Subjects will be instructed to avoid physical activity that would exceed their normal activity for 3 days before each visit.

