### **9.1.2 Visit 3 - Randomisation (Week 0)**

At Visit 3, the following assessments will be performed:

- Review eligibility criteria;

- Record prior medications;
- Perform a physical examination;
- Measure vital signs (blood pressure, pulse rate, and body temperature);
- Measure weight;
- Perform a 12-lead ECG;
- Collect blood samples for hematology;
- Perform LTBP4 and Osteopontin genotype tests and collect DMD serum biomarkers;
- Perform time to 4SC;
- Perform NSAA and 6MWT;
- Perform muscle strength test;
- Randomise the child and dispense and account for study drug;
- Subject diary dispensation
- Assess AEs.

Functional tests will be video recorded.

Pulmonary function as assessed by spirometry at screening should be repeated if the test does not meet ATS/ERS criteria and/or the evaluator deems that a valid attempt to perform a correct maneuver has not been made by the subject.

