### **12.3 Electrocardiogram**

A 12-lead resting ECG will be obtained at the visits indicated in the Schedule of Assessments, Table 6.

At the Screening Visit, the Investigator will examine the 3 ECG traces for signs of cardiac disease that could exclude the subject from the study. An assessment of normal or abnormal

will be recorded. If the ECG is considered abnormal, the abnormality will be documented on the CRF. If an ECG demonstrates a prolonged QTcF interval (i.e. >450 msec) at the defined timepoints (see Schedule of Assessments, Table 6), the Investigator will obtain 2 more ECGs over a brief period (5 minutes between recordings), and then use the averaged QTcF value of the 3 ECGs. If the averaged QTcF value meets the stopping criteria, the subject has to interrupt the study drug, the Medical Monitor must be informed and the mean QTcF value must be confirmed by central reading.

During the study, ECG should be performed at 2,5 hours  $\pm$  30 minutes after drug intake.

The QTc has to be calculated with the Fridericia formula  $QTc = QT/RR^{1/3}$ .

Electrocardiograms will be repeated if clinically significant abnormalities are observed or artifacts are present.

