5 SAFETY EVALUATION

All safety listings will be presented for the all enrolled subjects set and all safety tables and figures will be presented for the safety analysis set unless specified otherwise. Additionally, see Section 2.8 regarding use of the target versus overall population. Baseline is defined as the last non-missing value recorded prior to or on the date of first study treatment. Where the value is recorded on the same date as first study treatment and there is no further information to confirm whether this was prior to start of treatment, the value will be considered prior to treatment if this was a screening or randomisation assessment and otherwise will be considered post treatment.

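### The SAP's general safety baseline makes one Visit 3 tracing the usual QTcF baseline, which raises the background rate of >30 msec increases in both arms

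*SAP*

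**What the plan says.** **Replication.** Protocol Table 6, footnote 6, states: "12-lead ECG has to be done in triplicate at the screening visit and during the other visits if an ECG demonstrates a prolonged QTcF interval" above 450 msec. Section 9.1.1 repeats the triplicate for screening. The Visit 3 list in section 9.1.2 says only "Perform a 12-lead ECG". Section 12.3 gives the same 450 msec trigger for two further tracings.

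**Baseline.** SAP section 5: "Baseline is defined as the last non-missing value recorded prior to or on the date of first study treatment". A same-day value from the randomisation visit counts as pre-treatment unless other information shows otherwise.

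**Averaging and outliers.** SAP section 5.5: "Where triplicate ECG assessments have been performed, the mean of the non-missing values will be used in the analyses". It sets no ECG-specific baseline. It counts QTcF above 450, 480 and 500 msec and increases from baseline above 30 and 60 msec, by visit and overall. In the overall summary, one occurrence at any visit is enough.

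**Eligibility.** Exclusion criterion 16 (protocol section 7.2) limits baseline QTcF, taken there "as the mean of 3 consecutive readings 5 minutes apart".

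**The concern.** Together these rules make the single Visit 3 tracing the usual baseline for QTcF change. The screening triplicate, the only replicated pre-dose measurement that is planned for every subject, enters the change analysis only if Visit 3 is missing or is shown to be after the first dose.

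Two features add to the effect of the noise. One baseline error is shared by all nine on-treatment ECG visits (Visits 4, 7, 9 and 10 to 15), so a low reading has nine chances to create an outlier under the at-least-once rule. Re-reading is also one-sided: a Visit 3 value above 450 msec is repeated and averaged, while a falsely low value, the kind that creates a false increase, is not.

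At stake is how readable the >30 msec table is. Protocol section 4.2.2 asks for particular attention to QTc after 21 prolongation episodes in 15 subjects. The same section adds that 90% of the events came from oncology studies at the highest doses, and that none occurred in the previous DMD study.

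**Working it through.** The documents state no QTcF SD and no expected outlier rate, so there is no figure of the plan's own to reproduce. Everything below rests on assumed SDs.

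**Inputs**
- From the documents: three screening tracings; one Visit 3 tracing; one tracing at each of nine on-treatment visits; two more when a reading exceeds 450 msec; thresholds of 30 and 60 msec; at-least-once counting.
- Assumed: true mean 400 msec; between-subject SD 15; reading SD *r* within a visit and visit SD *v* between days, with (*r*, *v*) = (10, 8), (7, 6) and (12, 10) msec; no drug effect.

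**SD of change, ignoring the re-read rule**
- Visit 3 baseline: variance = 2(*r*² + *v*²).
- Mean of four pre-dose tracings (screening weight 3/4, Visit 3 weight 1/4): variance = (*r*² + *v*²) + *r*²/4 + *v*²(9 + 1)/16.
- (10, 8): 2 × 164 = 328, SD 18.1. Pooled: 164 + 25 + 40 = 229, SD 15.1. Reduction 16%.
- (7, 6): 170, SD 13.0. Pooled: 85 + 12.25 + 22.5 = 119.75, SD 10.9. Reduction 16%.
- (12, 10): 488, SD 22.1. Pooled: 244 + 36 + 62.5 = 342.5, SD 18.5. Reduction 16%.

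**Chance of a >30 msec increase at one visit**, 1 − Φ(30/SD), at (10, 8): 30/18.1 = 1.66 gives 4.9%; 30/15.1 = 1.98 gives 2.4%.

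**At-least-once rates.** These come from simulation (200,000 subjects per scenario, re-read rule applied, no drug effect). At (10, 8) the simulated one-visit rates are 4.8% and 2.3%, in line with the formula.

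| Reading / visit SD (msec) | >30 msec at any of nine visits, Visit 3 baseline | Same, mean of four |
|---|---|---|
| 7 / 6 | 6.5% | 2.4% |
| 10 / 8 | 22% | 15% |
| 12 / 10 | 34% | 28% |

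At (10, 8) the share with a >30 msec increase at two or more visits falls from about 10% to 4%.

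**>60 msec at any visit:** about 0.3% against 0.02% or less at (10, 8), and 1.9% against 0.3% at (12, 10).

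**When day-to-day variation dominates** (reading SD 6, visit SD 10), making Visit 3 triplicate would help little: 17.2% to 15.6%. Pooling screening with Visit 3 gives 12.3%, because it averages over two days.

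**The case against.** **The noise favours no arm.** This stands. The error is equal in both randomised arms, and mean change stays unbiased and only loses precision. Safety is evaluated descriptively, and no test or stopping rule in the documents uses QTcF change.

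**The stronger QT outputs are unaffected.** This also stands. The >450, >480 and >500 msec counts do not use baseline. The >500 msec stopping rule rests on averaged triplicates and central reading.

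**A reader might infer that a real drug effect is diluted.** The plan and the arithmetic do not support that as a general statement. With a true +10 msec shift at SDs (10, 8), the excess over placebo at one visit is larger with the single baseline, about 8.3 against 6.6 percentage points. At any visit it is smaller, about 23 against 28. At (7, 6) the any-visit excess is larger again, about 20 against 18. The direction depends on the unknown SDs and on which summary is read.

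**A reader might infer that the triplicate is thrown away, or that the SAP contradicts the protocol.** Neither follows. The triplicate decides eligibility and serves as the fallback baseline. Criterion 16 uses the word baseline for an entry test and does not define the analysis baseline.

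**The last pre-dose value is a uniform and defensible rule.** This is fair. Equal averaging of four tracings also gives three-quarters of the weight to a visit about 4 weeks (± 2) earlier. On-treatment tracings remain single unless above 450 msec, so at (10, 8) about 15% would still be flagged with no drug effect.

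**Conclusion.** The point holds as a question of precision and readability. The usual QTcF baseline is one unreplicated tracing although three more pre-dose tracings exist for each subject. This raises the no-effect rate of >30 msec increases equally in both arms. Under the assumed SDs the any-visit rate rises by about 4 to 7 percentage points, and pooling would cut the SD of change by about 16%. The >60 msec count moves little unless variability is high.

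The direction holds for any non-zero reading variability. The size does not come from the documents: the single-baseline rate alone runs from 6.5% to 34% across the assumed range. The absence of QTc events in the previous DMD study lowers the urgency. This is a cheap improvement to one safety table and not a threat to the trial's conclusions.

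**What to change.** In SAP section 5.5, define the baseline for QTcF change and for the >30 and >60 msec categories as the mean of all pre-dose tracings: the screening triplicate plus Visit 3, including any Visit 3 repeats. Keep the Visit 3 baseline as a second table. If the data are already unblinded, leave the planned table as it is and add the pooled baseline as a labelled sensitivity table. The SAP addendum already offers a route for such a change.

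The cost is one sentence, one derivation and one extra table, with no new data. The price is that the ECG baseline then departs from the general safety rule and leans on a visit about 4 weeks earlier. A variable-specific baseline has a precedent in SAP section 4.1, which sets one for the four-stair climb.

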5.6 Echocardiography

Summary statistics of echocardiography (ECHO) observed values and change from baseline by parameter and visit will be presented by treatment group for all subjects in the safety analysis set.

All echocardiography data will be listed in full.

5.7 Pulmonary Function Test

Pulmonary function test data (FEV1 (L), FVC (L), FEV1/FVC (%) and PEF (L/min)) including change from baseline will be summarised by visit and treatment group. Where multiple assessments have been performed at a visit, the best of the repeated assessments will be used for summaries. The best of the repeated assessments is defined for each parameter as the assessment with the maximum absolute value.

In addition, the percent predicted value of FEV1, FVC and PEF will be calculated at baseline and after 12 and 18 months of treatment according to the following rules. Where multiple assessments have been performed at a visit, the best of the repeated assessments will be used in the calculation according to the same approach as above.

- $FEV1\% = FEV1 * 100 / ((-0.7453 - (0.04106 * age)) + (0.004477 * (age^2)) + ((0.00014098 * (height^2))^1))$ (Hankinson, Odencrantz, & Fedan, 1999)
- $FVC\% = FVC * 100 / ((-0.2584 - (0.20415 * age)) + (0.010133 * (age^2)) + ((0.00018642 * (height^2))^1))$ (Hankinson, Odencrantz, & Fedan, 1999)
- $PEF\% = PEF * 100 / (-422.8 + 5.288 * height)$, (Buyse, et al., 2015).

In each of the above calculations, age refers to the age at the time of the pulmonary function test assessment, calculated in years and months from date of birth and assessment date. Date of birth will be subject to the rules given in Section 4.4.4.4 prior to this calculation. Height refers to the most recent non-missing height measurement in cm at the time of the pulmonary function test assessment.

Summary statistics of observed values and changes from baseline in FVC%, FEV1% and PEF% will be presented by visit and treatment group for all subjects in the safety analysis set.

Plots of the mean PEF, FVC, percent predicted PEF and percent predicted FVC over time will be produced by treatment group.

All pulmonary function test data, including calculated percent predicted values, will be listed. These listings will include the age and height at the time of each assessment, as well as the individual triplicate values and the selected best value where appropriate.

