### **5.2.3 Safety Endpoints**

The safety endpoints of this study are as follows:

- Number of subjects experiencing treatment-emergent adverse events (TEAEs) and serious adverse events (SAEs) (Baseline through end of study [EOS]);
- Type, incidence, and severity of TEAEs and SAEs (Baseline through EOS);
- Changes from baseline to end of study of:
  - Vital signs and clinical laboratory tests (blood chemistry and hematology);
  - Respiratory function evaluated by forced vital capacity (FVC), forced expiratory volume at 1 second (FEV1), FVC/FEV1, peak expiratory flow (PEF);
  - Cardiac function evaluated by ECG and echocardiogram (ECHO);
  - Cognitive function evaluated by the Raven coloured progressive matrices;
  - Weight, height, and body mass index (BMI);
- Evaluation of acceptability/palatability of the oral suspension.

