#### **12.5 Respiratory Function Test**

Forced expiratory volume at 1 second (FEV1), FVC, FEV1/FVC, and PEF, will be collected as per the site's standard process at the visits indicated in the Schedule of Assessments, Table 6 and more often if clinically indicated.

At each assessment, three studies with maximal effort will be attempted by each subject, and the experienced technician performing the testing will make the determination if the effort will be acceptable. All the study results will be recorded in the eCRF.

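### SAP 5.7 takes the largest single-blow FEV1/FVC as the best value, so the reported ratio is never below best FEV1 over best FVC and its level is biased upward

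*SAP*

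**What the plan says.** SAP 5.7 names four parameters, the ratio among them, to be reported with their change from baseline: "Pulmonary function test data (FEV1 (L), FVC (L), FEV1/FVC (%) and PEF (L/min)) including change from baseline". It then gives one selection rule for all of them: "Where multiple assessments have been performed at a visit, the best of the repeated assessments will be used for summaries". Best is the maximum, taken separately for each parameter: "The best of the repeated assessments is defined for each parameter as the assessment with the maximum absolute value". There is no exception for FEV1/FVC.

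Repeats are routine. Protocol 12.5 states "At each assessment, three studies with maximal effort will be attempted by each subject" and "All the study results will be recorded in the eCRF", so a ratio exists for each blow. Nothing in SAP 5.7 limits the choice to blows judged acceptable.

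Protocol 5.2.3 makes respiratory function a safety endpoint assessed as change from baseline, but prints the ratio upside down: "forced expiratory volume at 1 second (FEV1), FVC/FEV1, peak expiratory flow (PEF". The synopsis does the same. The visit procedures, Protocol 12.5 and the SAP all use FEV1/FVC.

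**The concern.** For FEV1, FVC and PEF the largest of several blows is the best effort. For a quotient, the largest value can come from a good numerator or from a poor denominator. A blow stopped early has a small FVC and hence a high FEV1/FVC, so the rule tends to favour the least complete exhalation. The best FEV1, the best FVC and the best ratio may then come from different blows, and the three figures in one table row need not agree.

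At stake is the accuracy of one descriptive safety summary. Table 14.3.8.1, the pulmonary function summary, goes to the IDMC at each safety review (SAP 7.6), and the sponsor receives blinded tables without listings at those reviews. The percent-predicted values in SAP 5.7 cover only FEV1, FVC and PEF, so they offer no alternative view of the ratio.

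**Working it through.** The documents give no figure for this point, so there is nothing to reproduce. The direction of the bias follows from algebra. Its size needs assumptions.

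**Direction.** Let j be the blow with the largest FEV1. Then

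max(FEV1_i / FVC_i) >= FEV1_j / FVC_j >= max FEV1 / max FVC,

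because FEV1_j = max FEV1 and FVC_j <= max FVC. This needs no distributional assumption, only that blow j has both values. A check on 1,000,000 random sets of three blows found no exception.

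**One visit (illustrative volumes).** Blows of 1.55/1.80 L and 1.52/1.60 L give 86.1% and 95.0%. The table would show FEV1 1.55, FVC 1.80 and a ratio of 95.0%, although 1.55/1.80 = 86.1%. The excess is 8.9 points.

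**Mean excess at one visit (assumed model).** Three blows, with half-normal shortfalls from FVC 1.80 L and FEV1 1.55 L, independent of each other. The comparator is best FEV1 / best FVC.

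| Shortfall SD, FVC / FEV1 | Mean excess of SAP ratio |
|---|---|
| 3% / 2% | 2.1 points |
| 5% / 3% | 3.7 points |
| 8% / 4% | 6.6 points |

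The blow with the maximum ratio was also the blow with the smallest FVC in about 77% to 82% of cases, so this is a tendency and not a certainty. The model does not rule out ratios above 100%, which slightly raises the third figure. A second model (true FEV1 1.5 L and FVC 1.7 L, within-visit CV 3% to 8%, FEV1–FVC correlation 0.3 to 0.9) gave an excess of 1.0 to 6.3 points.

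**Change from baseline (first model, true fall of 6.1 points).**

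| Shortfall SD, baseline then follow-up | Mean change under the SAP rule |
|---|---|
| 5%/3% then 5%/3% | -6.4 |
| 8%/4% then 8%/4% | -6.7 |
| 3%/2% then 8%/4% | -1.3 |
| 8%/4% then 3%/2% | -11.7 |

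With equal variability the bias nearly cancels. With unequal variability the error is 6.1 - 1.3 = 4.8 points one way or 11.7 - 6.1 = 5.6 points the other. Best FEV1 / best FVC is not perfect in this model either: it sits 0.3 to 1.2 points above the true ratio, so its change would shift by about 1.2 - 0.3 = 0.9 points in the same two settings.

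**Number of blows (second model, CV 5%, correlation 0.6, true fall of 5.9 points).** Three blows at both visits give -6.1; three then six give -4.5. Best FEV1 / best FVC gives -5.9 in both. The documents do not say whether the blows of a repeat test are pooled with the visit they replace, so the second case is a possibility only.

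**How large it can be in one boy (illustrative volumes).** Baseline blows of 1.50/1.70, 1.48/1.68 and 1.45/1.66 L give 88.24% under either rule. Follow-up blows of 1.30/1.70, 1.28/1.66 and a short 1.15/1.30 L give 88.46% under the SAP rule and 1.30/1.70 = 76.47% from the best values: a rise of 0.2 points against a fall of 11.8. A short blow at baseline would push the error the other way.

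**The case against.** The best defence is that the endpoint is a change, and the same rule applies at baseline, at follow-up and in both blinded arms. Where variability and number of blows are stable, a constant upward shift mostly drops out. This stands. A reader might infer that the rule hides respiratory decline, on the argument that effort becomes more erratic as boys weaken. No passage in either document says that blow-to-blow variability rises over time, and if it fell the rule would exaggerate the decline. Masking is possible, but it is not the expected result.

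Second, quality control should limit short blows. A technician judges each effort (Protocol 12.5), and tests that fail ATS/ERS criteria or lack a valid attempt are repeated (Protocol Table 6 note 7 and sections 9.1.2, 9.1.7 and 9.1.8). This reduces the problem. It does not remove it, because all results are recorded and SAP 5.7 does not confine selection to acceptable blows.

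Third, safety is evaluated descriptively (Protocol 13.9), the individual triplicates are listed, and FEV1 and FVC are summarised in their own right. This stands and limits the importance of the point.

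A reader might also take the inverted label in Protocol 5.2.3 to mean that the maximum would be applied to FVC/FEV1 and select the opposite blow. The SAP never does that, so the label is a clerical slip.

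**Conclusion.** The point holds as a small derivation fault. That the summarised FEV1/FVC is never below best FEV1 / best FVC is certain whenever the blow with the highest FEV1 has both values. The size is not known from the documents: 2.1 to 6.6 points in level is what the assumed half-normal shortfalls give, measured against best FEV1 / best FVC and not against the true ratio. The effect on change from baseline is close to nil under stable conditions and can go either way when variability or the number of blows differs between visits. No efficacy conclusion, test or stopping rule depends on it. The correction is worth making because a named safety endpoint would otherwise be reported at an inflated level and can contradict the two values it is built from.

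**What to change.** In SAP 5.7, restrict the maximum rule to FEV1, FVC and PEF, and define FEV1/FVC at each visit as best FEV1 divided by best FVC x 100.

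The cost is one line of text and one derivation, from data already in the eCRF. The sponsor has already used a SAP addendum to correct derivations of this kind, so a route exists. The small downside is that the two values may come from different blows; a footnote to the table can say so.

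Separately, align the FVC/FEV1 label in Protocol 5.2.3 and the synopsis to FEV1/FVC. Protocol 14.6.1 requires a written amendment for any change, so this clerical correction can wait for the next one.
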